13	RISKS AND BENEFITS.....	23
14	ETHICAL CONSIDERATIONS	23
14.1	SUBJECT CONSENT AND CONFIDENTIALITY	23
14.2	SUBJECT FINANCIAL RESPONSIBILITY AND STIPENDS	23
15	PUBLICATION PLAN	24
16	INTELLECTUAL PROPERTY AND PATENTS.....	24
17	LIST OF ABBREVIATIONS.....	24
18	BIBLIOGRAPHY	25

Study Summary

Title	BENEFITS OF MICROCOR (μ Cor TM) IN AMBULATORY DECOMPENSATED HEART FAILURE (BMAD Treatment)
Short Title	BMAD Treatment
ZOLL Protocol Number	90D0202
Study Design	Prospective non-randomized study
Study Duration	The study duration will last an estimated 2.5 years with 2 year estimated for enrollment
Study Center(s)	Up to 80 centers (International)
Primary Objective(s)	To assess investigator engagement of μ Cor system data in the context of heart failure management
Study Population	Subjects hospitalized for acute decompensated heart failure and enrolled in the study within 10 days post-hospital discharge. All subjects require an additional heart failure event within the previous 180 days.
Intervention	Subjects meeting the inclusion/exclusion criteria will wear the μ Cor for up to 90 days. During the study, face to face follow up will occur every 30 days. For all subjects, each scheduled clinic visit will include assessment of cardiac signs, symptoms, and any relevant clinically actionable events. The subject will be given a daily diary to track symptoms, hospital visits, medication changes, and all other heart failure related clinical events. Weekly phone calls to the subject will be given throughout the duration of the study to remind the patient to use the subject diary and to collect and record heart failure related clinical events. The subject's health care provider team will receive the μ Cor data through reports delivered to the team by an independent clinical review team. The data updates will allow the health care provider team to take action when the data indicate worsening heart failure, within the context of standard of care medical practice and patient specific parameters. Weekly data reports will be delivered to the investigators. Subjects will be contacted six months and one year from initial enrollment to assess the vital status of the subject, any heart failure related clinical events since the end of μ Cor wear, and any health care utilization since the end of μ Cor wear.
Study Size	A total of 300 subjects
Reference therapy	NA

1 Introduction

This document is a protocol for a human research study. This study is to be conducted according to US and international standards of Good Clinical Practice (International Conference on Harmonization ICHE6), the Code of Federal Regulations Title 21 parts 803 and 812, and other applicable government regulations.

1.1 *Background*

Annually, over 1 million patients are hospitalized with a primary diagnosis of heart failure (HF)¹. Despite improvement in outcomes with medical therapy, readmissions for acute decompensated HF are common and place a significant burden on the healthcare system. Therefore, strategies for outpatient monitoring and fluid management are needed to reduce HF hospitalizations. Rather than low cardiac output, the main reasons for rehospitalization are symptoms associated with pulmonary and systemic venous congestion due to elevated ventricular filling (end-diastolic) pressures². Remote monitoring of these pressure changes in addition to its surrogate measures, such as intrathoracic impedance, lung fluid levels, systolic time intervals, or the presence of abnormal heart sounds, may help to prevent hospitalization by detecting early evidence of HF decompensation^{3, 4, 5}. In addition, remote monitoring may lead to better access to care and coordination of services.

Given the anticipated importance of remote HF monitoring and fluid management, ZOLL has developed a novel radiofrequency (RF) based heart failure and arrhythmia management system (μ Cor Heart Failure and Arrhythmia Management System). Using the RF data, μ Cor provides an estimate of the thoracic fluid index (TFI). To calculate TFI, the thoracic fluid baseline is determined, and the normalized value is presented as TFI. In conjunction with standard clinical practice for patients with fluid balance issues, the direction of change of TFI over time may provide clinically useful information. In addition to TFI, the system records the electrocardiogram (ECG) through adhesive electrodes and respiration rate, activity, and posture through a tri-axial accelerometer. The purpose of this study is to assess investigator engagement of μ Cor system data in the context of heart failure management.

1.2 *Preclinical Data*

In animal testing, μ Cor's noninvasively determined RF thoracic fluid content was compared with invasive thermodilution extravascular lung water measurements (PiCCO - Pulson Medical Systems, Munich, Germany). Pulmonary edema was induced in 15 sheep by intravenous volume and pressure overload. μ Cor was placed on the left lateral torso of the sheep. The emitted and reflected RF signals are used by μ Cor to assess thoracic fluid. These readings were compared with the readings from the PiCCO device. Results of the study showed that all 15 sheep developed increases in left ventricular end diastolic pressure, and the onset of pulmonary congestion and edema. A consistent linear correlation ($r = 0.97$) between measurements of invasive lung water fluid and noninvasive thoracic fluid content was observed. μ Cor RF signals were able to detect dynamic accumulation of lung water in the range of 50-60 ml increments. The change in lung water needed to produce congestion was between 250-500 ml. The results of this study support the use of ZOLL's external RF sensor for high resolution and precise fluid monitoring.

1.3 *Clinical Data to Date*

NA

1.4 Study Device

1.4.1 System Components

µCor consists of the following components:

- A) Patch
- B) Sensor
- C) Charger
- D) Data transmission device (Gateway)
- E) Server

Once activated, the wearable Sensor automatically acquires ECG, RF readings, heart rate, respiration rate, activity, and posture measurements. Data are automatically transmitted from the Sensor to the Data transmission device, and from there to the Server for analysis (see Fig. 1).

Figure 1: Data transmission of µCor

1.4.2 Patch

The Patch (Fig. 2) consists of a plastic frame intended for housing the Sensor, and two ECG electrodes on each side of the frame. The Patch is a single-use, disposable item.

[figure not shown]

Figure 2: Patch

1.4.3 Sensor

The Sensor (Fig. 3) is a battery powered unit that acquires data. The Sensor connects to the Patch via the snap-in clip and positioning tabs. Through the adhesive backing on the Patch, the

device becomes wearable. The Sensor is not disposable and needs to be returned to ZOLL upon the completion of the study. A light indicator is located close to the center and serves to communicate the Sensor's status at different points of use. Note that the light indicator is visible only when lit.

[figure not shown]

Figure 3: Sensor's front view

1.4.4 Charger

A dedicated Charger (Fig 4) is supplied with the μ Cor System for recharging the Sensor and the Data Transmission Device. A blue light appears when the Charger is connected to an AC outlet.

Figure 4: Charger

1.4.5 Data transmission device (Gateway)

A Data Transmission Device or Gateway is responsible for sending data from the Sensor to the Server for data analysis. When the screen display is on, the gateway battery status is visible on the screen. Once the battery status is under a certain level, a short beeping sound will be made every few minutes until the battery is depleted or the Gateway is placed in the Charger.

[figure not shown]

Figure 5: Gateway

1.4.6 Server

The Server refers to the hardware and the processing software and resides in a remote cyber-secure location. The software analyzes the data received from the Sensor via the Gateway and processes the data into clinical values.

1.4.7 Device (Sensor +Patch) Placement Location

The location of the patch is along the left anterior axillary line in line with the nipple.

[figure not shown]

Figure 6: Device (Sensor + Patch) placement location.

2 Study Objectives

2.1 Primary Objective(s)

The following primary objectives will be evaluated during BMAD-Treatment:

2.1.1 To assess investigator engagement of μ Cor system data in the context of heart failure management

2.2 Secondary Objective(s)

The specific secondary objectives that will be evaluated during the entire study include:

2.2.1 To identify correlations between μ Cor measurements (physiologic variables including thoracic impedance, cardiac rhythm, respiration rate) and heart failure related clinical events. A heart failure related clinical event is defined in section 6.1.3.

2.2.2 To identify correlations between μ Cor measurements (physiologic variables including thoracic impedance, cardiac rhythm, respiration rate) and patient reported symptoms.

2.2.3 To identify the hospital readmission rate, physician visit rate, and outpatient clinic visit rate of subjects during the study period.

2.2.4 To identify the mortality rate, cause of death, quality of life (QoL), and health care utilization among patients six months and one year after enrollment into the study.

2.3 Safety Objective(s)

2.3.1 To document the number and severity of all adverse events that are causally related to the μ Cor system or study specific procedure.

2.4 Additional Objective(s)

NA

3 Study Design

3.1 General Design

3.1.1 Study Description

Subjects meeting the inclusion/exclusion criteria will wear μ Cor for up to 90 days from the day of fitting. 300 total patients will be enrolled. Subjects will be fitted with μ Cor during discharge of a heart failure related hospitalization or within a clinic visit that has occurred within 10 days of a heart failure related hospitalization. The μ Cor fitting will mark day 0 of the study. An LVEF measurement will be recorded during enrollment or within 30 days post enrollment if an LVEF measurement has not been recorded within 30 days prior to enrollment. Any LVEF will qualify for the study. An investigator assessment will be performed during all clinic visits. The assessment template is shown in Appendix A.

Subjects will be given a diary at enrollment that will ask them to rate their degree of specific symptoms of heart failure such as shortness of breath and fatigue as well as mark any heart failure related clinical events or medication changes that have occurred since the last entry. The subject diary is shown in Appendix A.

Phone calls will be based on weekly data reviews or data updates. A review of the data will be conducted by the site before the weekly phone call and the most recent (Transthoracic Fluid Index) TFI will be recorded. The subject will receive a study based weekly phone call asking the subject about any recent heart failure related clinical events or change in heart failure symptoms. The weekly phone calls will continue if the subject has stopped wearing the device. During the weekly phone call the subject will be reminded to fill out the daily diary. No phone calls will be given on the week where there is a study follow up visit.

A review of the data will be conducted by the site before the office visit and the most recent TFI will be recorded. Study face to face follow up visits will occur at day 30, day 60, and day 90. There will be no follow up visit if the subject has stopped wearing the device. During follow up visits the subjects will be asked about any heart failure related clinical events or change in symptoms that have occurred since the last follow up.

Unplanned visits to the physician office or hospital will be captured and defined as visits that the subject did not plan beyond 48 hours. In case of adverse skin reaction to the μ Cor adhesive and/or electrodes, on the discretion of physician, subjects may discontinue wearing the device for up to 48 hours. In the event the subject has stopped wearing the device completely, follow up phone calls will continue to be conducted per protocol in order to capture clinical information.

During the Day 90 visit, the subject will be given the option to continue wearing the μ Cor for an additional 90 days. Furthermore, if the subject experienced a heart failure related clinical event within the initial 90 days of wear, the subject will be given the option of wearing the μ Cor for 30 days following the heart failure event. If the subject chooses additional wear time, weekly phone calls and monthly visits will be structured identical to that of the main study period. The μ Cor will be returned at end of use.

Data updates will be delivered to the site when the day averaged TFI exceeds a threshold greater than three standard deviations of the baseline TFI level for three consecutive days. Upon receiving a device data update, the investigator will receive detailed information into how the device measurements have tracked over the days leading up to the notification. When receiving a data update, the site will be required to review the most recent report within 24 hours, and explain their reasoning whether they choose to contact the subject or not to contact the subject. The data review must occur prior to every scheduled subject contact.

When acting upon the data update, the site may contact the subject to assess the subject's current symptoms and history, and make an informed decision within the context of both device measurements and standard medical care as to what actions to take with the subject. Potential actions the site could take will include, a prescription drug change or titration, a request for an office visit, a request for hospitalization, and request for lifestyle or diet modifications. The site will document any changes to subject care within the case report forms. Unscheduled contacts that the subject initiates will be recorded as well.

There will be a follow up at six months and one year post enrollment to document mortality data, heart failure related clinical events, and health care utilization data. A timeline visualization of the study procedure is shown in Figure 7.

[figure not shown]

Figure 7: Procedure Flow of BMAD Treatment Study

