6.2 Scheduled Visits and Phone Calls

The scheduled visits are summarized in Table I and include the initial face to face visit along with face to face visits at day 30, 60, and 90. There will also be weekly phone calls to the patient. No monthly visits will occur if the subject has stopped wear. The phone calls will be conducted within no more than 2 days before or after the scheduled date. The scheduled visits will be conducted within no more than 5 days before or after the scheduled date. During subject wear, phone calls will be accompanied by the weekly data review. The data review will need be completed before the phone call. There will be a weekly report sent to the site.

During the optional extended 90 day wear period, scheduled clinic visits and weekly phone calls will continue to take place following the procedures in Visits 2-4 with the exception of 6.2.4.6 (asking again for additional wear). Chart review, study questionnaires, and a follow up phone call will take place at 6 months and 1 year post enrollment.

6.2.1 Visit 1: Screening, enrollment and start (To occur during hospital discharge for decompensated heart failure or during a clinic visit in an out-patient setting no more than 10 days post hospital discharge).

- 6.2.1.1 Patients meeting the initial Inclusion/Exclusion criteria will be approached for consenting.
- 6.2.1.2 All subjects will complete the Kansas City HF Questionnaire and study specific questionnaire.
- 6.2.1.3 A chart review will be used to evaluate patients for enrollment. A screening log will be maintained.
- 6.2.1.4 The initial clinical and demographic data will be recorded in every subject. These may be done by chart review and will include:
 - 6.2.1.5 Demographic characteristics, including gender, age, and height will be recorded.
 - 6.2.1.6 Medical history will be recorded, including comorbidities, heart disease and physical disability.
 - 6.2.1.7 All medications will be recorded.
 - 6.2.1.8 LVEF measurement within the past 30 days will be recorded if available. If a previous LVEF is not available, one will be obtained within 30 days of enrollment.
 - 6.2.1.9 Subjects will be given a physical assessment.
 - 6.2.1.10 (US Sites) Device training will be given to the subject.
 - 6.2.1.11 (European Sites) Subjects will be fitted with μ Cor at hospital discharge or departure from clinic.
 - 6.2.1.12 (European Sites) Device fitting will follow current Instructions for Use (IFU)

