 - 6.2.1.13 (European Sites) The date and time when μ Cor wear began will be recorded.
 - 6.2.1.14 A clinic visit appointment will be scheduled to coincide with the end of the first 30 days of μ Cor wear.

- 6.2.1.15 The subject's weight will be obtained.
- 6.2.1.16 The subject's previous 90 day hospital admission rate will be determined through chart review.

6.2.2 Visit 2: μCor Wear Day 30.

- 6.2.2.1 All subjects will complete the Kansas City HF and study specific questionnaire.
- 6.2.2.2 An in-center appointment will be scheduled to coincide with the end of 60 days of μCor wear.
- 6.2.2.3 All subjects will be asked about the following events since their last visit:
 - Any physician visits, both planned and unplanned
 - Any hospitalization, including heart failure hospitalization
 - Any emergency room visits
 - Any symptoms, including syncope, dyspnea, palpitations and chest pain
- 6.2.2.4 A weight measurement will be obtained.
- 6.2.2.5 Subjects will be given a physical assessment
- 6.2.2.6 Daily cardiac medications taken by the subject will be reviewed and compared to the last listed cardiac medications documented by the study. Any new cardiac medications or changes in medication will be recorded (i.e. dosage changes or new medications administered)

6.2.3 Visit 3: μCor Wear Day 60.

- 6.2.3.1 All subjects will complete the Kansas City HF and study specific questionnaire.
- 6.2.3.2 An in-center appointment will be scheduled to coincide with the end of 90 days of μCor wear.
- 6.2.3.3 All subjects will be asked about the following events since their last visit:
 - Any physician visits, both planned and unplanned
 - Any hospitalization, including heart failure hospitalization
 - Any emergency room visits
 - Any symptoms, including syncope, dyspnea, palpitations and chest pain
- 6.2.3.4 A weight measurement will be obtained.
- 6.2.3.5 Subjects will be given a physical assessment.
- 6.2.3.6 Daily cardiac medications taken by the subject will be reviewed and compared to the last listed cardiac medications documented by the study. Any new cardiac medications or changes in medication will be recorded (i.e. dosage changes or new medications administered)

6.2.4 Visit 4: μCor Wear Day 90.

- 6.2.4.1 μCor use will be discontinued unless subject enters optional additional wear period.
- 6.2.4.2 All subjects will complete the Kansas City HF and study specific questionnaire.
- 6.2.4.3 All subjects will be asked about the following clinically actionable events:

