6.4 Long-term Clinical Outcome Assessment

The subject will receive a follow up phone call 6 months (180 days) and 1 year (365 days) from the enrollment date to assess for mortality status, heart failure related clinical events that have occurred since the end of μCor wear, and any health care utilization that has occurred since the end of μCor wear. A chart review will be performed during both of these calls as well. Subjects will answer mailed heart failure questionnaires and mail the questionnaires back to the site. These follow-up calls must occur within +/- 2 weeks of the scheduled call.

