8.7 Futility Analysis

NA

9 Health Economic Evaluation

The Kansas City Heart Failure Questionnaire and study specific questionnaire will be administered to subjects during monthly clinic visits. We will develop a model to examine the costs and benefits of using uCor. The model will use health care utilization data from weekly and monthly questionnaires, as well as data from recognized sources (e.g. national published data, finance department of hospital), and experts' advice.

10 Safety and Adverse Device Effects

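### The day 30, 60 and 90 questionnaires are tied to visits that are cancelled once wear stops, so the monthly scores describe continuing wearers only, with a bias of unknown direction

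*Combined protocol and SAP*

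**What the plan says.** Section 3.1.1 sets face-to-face visits at days 30, 60 and 90 and then limits them: "There will be no follow up visit if the subject has stopped wearing the device". Section 6.2 repeats the rule: "No monthly visits will occur if the subject has stopped wear".

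The items for Visits 2, 3 and 4 (sections 6.2.2 to 6.2.4) each state: "All subjects will complete the Kansas City HF and study specific questionnaire". Section 9 confirms where this happens, since the Kansas City and "study specific questionnaire will be administered to subjects during monthly clinic visits". Weight, physical assessment and the cardiac medication comparison are listed under the same visits. For the congestion survey in Appendix A, section 3.1.1 says: "An investigator assessment will be performed during all clinic visits".

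Some collection does not depend on wear:

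- Section 3.1.1: "The weekly phone calls will continue if the subject has stopped wearing the device". With section 6.6, these calls cover heart failure events, change in symptoms, health care use and a reminder about the diary.
- Section 6.4 plans a call and a chart review at 6 months and 1 year, and adds: "Subjects will answer mailed heart failure questionnaires and mail the questionnaires back to the site". It sets no wear condition.

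The listed quality-of-life endpoint (sections 3.3.4 and 8.3.2.4) is at 6 months and 1 year. On the cost model, section 9 says: "The model will use health care utilization data from weekly and monthly questionnaires". Section 8.6.3 rules out imputation, and section 8 gives no rule on denominators or on summaries by wear status.

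**The concern.** A questionnaire said to be completed by all subjects cannot be completed at a visit that some of them will not have. If sites follow the visit rule, a subject who stops on day 20 has no Kansas City score at days 30, 60 or 90, although that subject is still in the study and is still being phoned.

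The missing scores are selected on tolerance of the device, which is the thing under study. Two uses of the data are exposed:

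- **A score series over time.** Baseline covers everyone, days 30 to 90 cover wearers, and 6 months and 1 year cover everyone again. A change between day 90 and 6 months could come purely from the change in who is counted.
- **The cost model in section 9.** It draws on the monthly questionnaires, and that part of its input is absent for stoppers.

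Scores that were never collected cannot be recovered at the analysis stage.

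**Working it through.** **Step 1: is there another route to these questionnaires for a stopper at days 30, 60 and 90?**

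| Route | What the plan provides | Reaches a stopper's questionnaire? |
|---|---|---|
| Clinic visit (6.2.2 to 6.2.4) | Questionnaires listed here | No, visit cancelled (3.1.1, 6.2) |
| Weekly call (3.1.1, 6.6) | Events, symptom change, health care use, diary reminder | No, questionnaires not among the contents |
| Diary (Appendix A) | 0 to 10 ratings of four symptoms, hospitalization, medication change | No, a different instrument |
| Mail (6.4) | Heart failure questionnaires | Only at 6 months and 1 year |
| Visit procedure list (6.5, Table 1) | No questionnaire row | No |

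The plan as written therefore collects them from continuing wearers only. A related gap is that section 3.1.1 skips the weekly call in any week with a study visit, and does not say whether a stopper, who has no visit, is called in that week.

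**Step 2: how large could the bias be?** The documents state no figure for this point, so there is none to reproduce. Let d be the share who have stopped by a visit, W the mean score in wearers and S the mean in stoppers. The mean over all subjects is (1 - d)W + dS. The reported mean is W. Hence

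bias = W - [(1 - d)W + dS] = d × (W - S).

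**Inputs.** The 300 subjects come from section 5.2. Neither d nor W - S is in the documents. Both are assumed here: d from 10 to 40%, and W - S from -10 to +15 points on a score where higher is better. Deaths and other losses are left out.

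| d | Subjects with visit scores, 300 × (1 - d) | W - S = -10 | -5 | 0 | +5 | +10 | +15 |
|---|---|---|---|---|---|---|---|
| 10% | 270 | -1.0 | -0.5 | 0 | 0.5 | 1.0 | 1.5 |
| 20% | 240 | -2.0 | -1.0 | 0 | 1.0 | 2.0 | 3.0 |
| 30% | 210 | -3.0 | -1.5 | 0 | 1.5 | 3.0 | 4.5 |
| 40% | 180 | -4.0 | -2.0 | 0 | 2.0 | 4.0 | 6.0 |

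The extremes are 0.4 × (-10) = -4.0 and 0.4 × 15 = +6.0. The sign is set entirely by W - S.

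**Step 3: which analyses use these scores?** The primary endpoint (3.2.1, 8.3.1) counts data updates, review time, medication changes, lifestyle advice and returns below threshold, with no questionnaire. The quality-of-life endpoint uses 6 months and 1 year, where collection ignores wear. What remains is any summary of the day 30, 60 and 90 scores and the monthly questionnaire input to section 9.

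**The case against.** The strongest reply is that no listed endpoint depends on the scores that are lost, and that stoppers are otherwise well followed. Weekly calls record their events, symptom changes and health care use, the diary is still prompted, and the 6-month and 1-year contacts ask about events and use since wear ended and add a chart review. All of this stands, and it confines the point to the monthly visit data.

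Three stronger readings are tempting, and the documents support none of them.

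- **A reader might infer that the monthly scores will look better than the full cohort.** That is plausible in patients recently discharged after decompensation, but no section says who stops or why. Stopping for rash or burden does not in itself mean worse heart failure. Section 3.1.1 allows a pause of up to 48 hours for skin reactions, so a rash need not end wear. Subjects who stop because they feel well would push the bias the other way.
- **A reader might take the expected wear of over 70% in section 7.1 to mean that up to 30% will stop.** That figure is wear time. Every subject could wear the device for 75% of the time and no visit would be lost.
- **A reader might conclude that the cost model rests on adherent subjects only.** Section 9 names health care utilization as the input, from weekly as well as monthly questionnaires, together with outside data and expert advice. It does not name Kansas City scores as a model input. Utilization in stoppers is still captured by the calls and the later contacts, so only the monthly questionnaire part is missing.

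The ban on imputation in section 8.6.3 is not the fault either. The gap lies in collection, and the remedy needs no imputation.

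**Conclusion.** The point holds within limits. The no-visit rule is stated twice, the questionnaires are placed at those visits, and no other route reaches stoppers on those days, so the passages contradict one another on who completes them. Followed as written, the plan gives monthly scores from continuing wearers only.

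On the assumptions above, the bias in a monthly mean lies between about -4 and +6 points, and is zero if wearers and stoppers do not differ. Its direction is unknown, though a favourable one is plausible. The harm is limited to the day 30, 60 and 90 questionnaire data and the monthly questionnaire inputs to section 9. It is worth correcting because the correction is cheap and the data cannot be obtained later.

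**What to change.** Reconcile sections 3.1.1, 6.2 and 9 by stating that the day 30, 60 and 90 questionnaires go to every subject still in the study, whether or not they are wearing the device. For stoppers, use mail, as section 6.4 already does, or the weekly call. State that a stopper is still called in a week when a visit would have fallen.

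In addition:

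- Record the mode of administration, and the date and reason for stopping wear.
- Report scores at each time point for all subjects and by wear status, with denominators and deaths.
- Label the congestion survey, physical assessment and other clinic measurements at these visits as coming from continuing wearers. This change does not recover them for stoppers.

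A mixed model on the observed scores would be compatible with section 8.6.3, but it is optional in a descriptive study.

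The cost is up to three mailings or phone administrations for each stopper, who is already being phoned weekly. It needs no extra clinic visit. The downside is that mode of administration will differ between wearers and stoppers, which is why it should be recorded.
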